Visit 1 (ECV Procedure): The PI/Sub-I will meet the patient at the labor and delivery area, and review both the ECV procedure and possible study inclusion. The patient and researcher will sign consent forms if the patient qualifies for study inclusion and agrees to participate.

After weighing the patient, calculating a body mass index, performing a digital cervical exam, and performing a fetal non-stress test and obstetric ultrasound, all routine components of the ECV process, the PI/Sub-I will verify there are no exclusion criteria. Assuming that an ECV is still necessary and safe, the patient will receive a 0.25mg subcutaneous injection of terbutaline, a medication to quiet the uterus that is commonly used for ECV procedures. The midwife/physician performing the device inflation or sham inflation will open the randomization envelope. The researchers are blinded to patient randomization. All patients will mark a line on a 100mm VAS to assess pre-procedure pain.

The researcher will show the patient the device, open the sterile container, and insert the device into the vagina per manufacturer's guidelines for all patients in the study. All patients will mark a line on a 100mm VAS to assess post-insertion pain. The study physician will then obtain the assistance of a trained midwife/physician to inflate the device or perform a sham inflation. For the physician to remain blinded, the physician will leave the room during the time of the inflation/sham inflation. This will be documented in the source documents. Midwives/Physicians performing the inflation or sham inflation will have undergone previous training. Inflating the

Fetal Pillow is similar, although less difficult, than other balloon devices commonly used on the labor and delivery unit. The assisting midwife/physician will inflate the device with 180 mL of saline for those patients randomized to inflation. This will occur under a sheet so that the patient is blinded to the randomization scheme. If the patient is randomized to no inflation, the midwife/physician will perform a sham inflation, also under a sheet. All patients will mark a line on a 100mm VAS to assess post-inflation/sham inflation pain. The assisting midwife/physician then leaves the room, and the study physician reenters the room and proceeds with the ECV procedure.

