Maternal and neonatal outcomes will be analyzed using chi-square and Fisher exact tests for categorical variables, unpaired t-tests for continuous variable, and non-parametric tests for continuous variables that are not normally distributed. P values <0.05 will be considered statistically significant.

Potential Risks and Benefits

Potential Benefits

The Fetal Pillow device may improve the ECV success rate.

Potential Risks

Although unlikely based on prior device usage during 2nd stage arrest, it is possible the device may cause vaginal bleeding, increased pain during the procedure, or either no change in success or a lower success rate compared to performing the procedure without the device. Terbutaline administration may cause maternal tachycardia, irritability, chest pressure or chest pain. While loss of confidentiality is a potential risk to patients, patient information will be de-identified prior to analysis and only study personnel will have access to patient information. The United States Food and Drug Administration has determined that this study protocol is a nonsignificant risk (NSR) study (Review # Q191927, notification received December 18, 2019).

Mitigation of Risks

Patients will be asked prior to administration of terbutaline if they have contraindications, which is standard practice prior to using this medication.

Provisions to Protect the Privacy Interest of Subjects

The steps to protect the privacy of subjects have been described previously. Briefly, study documentation and patient information will be stored in a separate file on a password-protected laptop stored in a locked office. Drs. [name], [name] and research team will have access to both files.

Early Withdrawal of Subjects

Investigator Withdrawal of Subjects.

Inability to place Fetal Pillow: If the Fetal Pillow cannot be placed, for example due to pain, or the Fetal Pillow cannot be inflated, the patient will be withdrawn from the study. However, she may undergo an attempted ECV outside of the study protocol if she wishes.

Delivery at a hospital outside of the AdventHealth Orlando system: If the patient delivers outside of the AdventHealth Orlando system she will be withdrawn from the study analysis.

Subject Request for Withdrawal from Study

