Patient requests withdrawal: Patients who request withdrawal for any reason will be immediately withdrawn. If a patient initially consents to have the Fetal Pillow placed, then changes her mind before or during the procedure, the researcher will remove the device and offer the patient the opportunity to proceed with an ECV attempt off-protocol. Researchers will ask the patient if they can complete data collection for delivery and proceed according to the patient's wishes. There are no known or suspected harms from withdrawing from the study.

Data Collection and Follow-up for Withdrawn Subjects

Patients electing to withdraw from the study will be asked if they consent to data collection for delivery. If they decline this, then data collection will discontinue, and the data collection sheet will be stored as deidentified data in case the patient's reason for withdrawal (for example, excessive pain) is identified as a side effect of the device. The percentage of patients withdrawing and the reasons for withdrawal will be calculated and included in any manuscript submissions.

Adverse Event Reporting

Adverse events will be collected from the time of insertion up to 1 hour after the ECV procedure and followed until discharge. Adverse events such as excessive pain or bleeding will be recorded as part of the data collection. Adverse events of special interest will be reported according to AdventHealth Orlando IRB policies

Adverse events of special interest include:

Term	Mild	Moderate	Severe	Serious	Serious
------	------	----------	--------	---------	---------

Vaginal Hemorrhage	Mild symptoms; intervention not indicated	Moderate symptoms; intervention indicated	Transfusion indicated; invasive intervention indicated; hospitalization	Life-threatening consequences; urgent intervention indicated	Death
Pelvic Hematoma	Mild symptoms; intervention not indicated	Minimally invasive evacuation or aspiration indicated	Transfusion; invasive intervention indicated	Life-threatening consequences; urgent intervention indicated	Death
Vaginal Laceration	Separation of the perineal skin only	Injury to the perineal muscles but not the sphincter or rectum	Injury to the perineal muscles and anal sphincter	Injury to the perineal muscles, sphincter, and rectal mucosa	Death

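### The randomization envelope is opened before a device insertion that both arms share, so failed placements become avoidable post-randomization withdrawals

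*Combined protocol and SAP*

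**What the plan says.** Study Visits, Visit 1 (ECV Procedure), describes the day in this order: exclusions checked, terbutaline given, envelope opened, pre-procedure VAS, device inserted, post-insertion VAS, inflation or sham inflation, ECV. On the envelope it says "The midwife/physician performing the device inflation or sham inflation will open the randomization envelope", followed at once by "The researchers are blinded to patient randomization".

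Insertion is common to both arms: the researcher is to "insert the device into the vagina per manufacturer's guidelines for all patients in the study". Only after the post-insertion VAS does the text bring in the person who needs the allocation: "The study physician will then obtain the assistance of a trained midwife/physician to inflate the device or perform a sham inflation". The control condition also begins there: "If the patient is randomized to no inflation, the midwife/physician will perform a sham inflation, also under a sheet".

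Early Withdrawal of Subjects then states: "If the Fetal Pillow cannot be placed, for example due to pain, or the Fetal Pillow cannot be inflated, the patient will be withdrawn". An ECV outside the protocol remains possible for her. The subject-request part covers a woman who "changes her mind before or during the procedure"; she too may go on to an off-protocol attempt.

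The Statistical Analysis Plan names chi-square and Fisher exact tests for the primary outcome. It defines no analysis population and gives no rule for women withdrawn after randomization.

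**The concern.** Allocation is revealed several steps before anyone has to act on it. A woman whose device cannot be placed, or who changes her mind before inflation, leaves the trial before any difference between the arms exists. Under the written order she has nevertheless been randomized.

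That leaves two options, neither of them clean. If she is excluded, the analysed set is no longer the randomized set. If she is kept by intention to treat, she contributes no contrast between the arms and dilutes the effect. Keeping her is also not secured in practice: withdrawing women are asked only about data collection for the delivery, so nothing ensures that the result of an off-protocol ECV, which is the primary outcome, is recorded. Opening the envelope after insertion removes the dilemma for these women.

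**Working it through.** **Sequence.** The order comes from the Visit 1 narrative.

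| Step | Differs by arm? | Allocation needed? |
|---|---|---|
| Envelope opened | no | no |
| Pre-procedure VAS | no | no |
| Insertion by the blinded researcher | no | no |
| Post-insertion VAS | no | no |
| Assistant called; inflation or sham | yes | yes |

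The Randomization section asks only that an unblinded practitioner fetch the envelope from the locked cabinet. It gives no reason for opening it before insertion.

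**The plan's own figure.** Inputs from Sample Size Determination: p1 = 0.49, p2 = 0.735, two-sided 5%, 80% power, 1:1 allocation, 10% dropout.

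- Pooled formula: n = [1.960·√(2·p̄(1−p̄)) + 0.842·√(p1(1−p1) + p2(1−p2))]² / (p2−p1)². Here p̄ = 0.6125, p̄(1−p̄) = 0.2373, p1(1−p1) = 0.2499, p2(1−p2) = 0.1948 and p2−p1 = 0.245. This gives n = 60.9.
- With continuity correction: (n/4)·[1 + √(1 + 4/(n·0.245))]² = 68.8, so 69 per arm. The stated figure reproduces.
- Dropout: 69 × 1.10 = 75.9, so 76 per arm and 152 in total, as stated.

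**Power with no placement failures.** Power = Φ{[d − 1.960·√(2p̄(1−p̄)/n)] / √([p1(1−p1) + p2(1−p2)]/n)}, where d is the difference in success rates. At n = 76 this is Φ{(0.245 − 1.960 × 0.0790)/0.0765} = Φ(1.18) = 88.1%.

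**Power with placement failures.** Let f be the failure rate, equal in both arms. The documents give no value, so 2%, 5% and 10% are assumed. If these women are kept, with 49% success assumed in both arms, the inflation-arm rate becomes p2′ = (1−f)·0.735 + f·0.49. At f = 5% this is 0.72275, and power is Φ{(0.23275 − 1.960 × 0.0793)/0.0770} = Φ(1.01) = 84.3%.

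| f | p2′ | Current order, kept by ITT, 76 per arm | Current order, excluded | Opened after insertion, 152 consented | Opened after insertion, 152 randomized |
|---|---|---|---|---|---|
| 2% | 0.7301 | 86.6% | 74 per arm, 87.2% | 74 per arm, 87.2% | 88.1% |
| 5% | 0.7228 | 84.3% | 72 per arm, 86.3% | 72 per arm, 86.3% | 88.1% |
| 10% | 0.7105 | 79.9% | 68 per arm, 84.2% | 68 per arm, 84.2% | 88.1% |

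The last column requires 152/(1−f) consents: 152/0.98 = 155.1, 152/0.95 = 160.0 and 152/0.90 = 168.9. That is about 4, 8 or 17 extra women.

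The comparison that isolates sequence is the third column against the fifth, at the same 152 consents: 0.6, 2.0 and 4.3 points. Against exclusion (fourth column), sequence alone changes power by nothing.

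**The case against.** The strongest case against has four parts.

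- **Power.** A reader might infer that re-sequencing by itself buys 3 to 5 points of power, because exact Fisher power is 85.2% at 76 per arm, 82.2% at 72 and 79.9% at 69. The documents do not support that. If 152 women consent and 8 cannot have the device placed, 144 are analysed whether the 8 were excluded after randomization or never randomized. The higher figure comes from recruiting replacements. The 10% allowance is also there to absorb losses down to 69 per arm. This objection stands; what remains is the dilution under intention to treat.
- **Bias.** A reader might infer that decisions to persist with or abandon insertion are influenced by a team member who knows the allocation. The text points the other way: the researcher who inserts is blinded, the patient is blinded, and the assistant is called in only after insertion. Nothing gives the assistant a part in that decision. This objection stands too, and balanced losses should be expected.
- **Reach.** A reader might infer that the change makes the randomized and analysed sets equal. It does not. Failed inflation, which is also a ground for withdrawal, follows allocation and can occur only in the inflation arm. Changes of mind after inflation and the withdrawal of women who deliver elsewhere also remain. An analysis-population rule is the larger need.
- **Timing.** No sentence says the envelope is opened before insertion; the order is read from the narrative, and the envelope sentence could be taken as only assigning a role. That is fair, but a site following the text in order would open it early, so the wording needs changing either way.

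**Conclusion.** The point holds, at modest size. As written, women lost between envelope opening and inflation are randomized needlessly, because insertion is identical in both arms. The consequence is an analysed set that departs from the randomized one or, under intention to treat at 76 per arm, chi-square power of 86.6%, 84.3% or 79.9% instead of 88.1%, for assumed failure rates of 2%, 5% or 10%. These figures assume equal failure rates in the two arms and 49% success in the affected women. If placement almost never fails, the effect is close to nil. No bias is shown.

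Study Site/Location and Number of Subjects gives 138 rather than 152. At 69 per arm the corresponding figures are 83.2%, 80.6% and 75.9%, against 84.8% with no failures, so there is less room to absorb the loss.

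**What to change.** In Visit 1, have the envelope fetched in advance but kept sealed, and opened when the assistant is called to inflate, after successful insertion and the post-insertion VAS. Define the randomized population from that moment, and edit the failed-placement wording under Early Withdrawal to match.

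Record women with failed placement as not randomized, but still count them and report them for safety, because Adverse Event Reporting starts collection at insertion.

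Add the rule that re-sequencing cannot supply: women with failed inflation, or withdrawn after inflation, are analysed in their randomized arm, and their ECV result is collected.

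The cost is a moved sentence, two matching edits and a few more consents to reach the randomized target. The results will also apply to women in whom the device can be placed, which the report should say.

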3. EGA
4. Name of obstetrician performing ECV procedure
5. Presence of inflated Fetal Pillow
6. Presence of terbutaline
7. Presence of palpable fetal head
8. Estimated fetal weight (kg)
9. Fetal head position *confirmed by ultrasound
10. Fetal back position
11. Position of fetal neck
12. Location of placenta
13. Amniotic fluid index (4 quadrant total)
14. Fetal station (-3 through +3)
15. Maternal cervical dilation (cm)
16. Presence of rupture of membranes within 1 hour of procedure
17. Presence of 3 or more contractions in 10 minutes immediately prior to procedure
18. Bleeding equal to a menstrual period during or within 1 hour of the ECV procedure.
19. Development of a pelvic hematoma during or within 1 hour after the ECV procedure.
20. Development of a vaginal laceration during insertion of the device, the ECV procedure, or removal of the device.
21. Presence of fetal bradycardia
22. Presence of fetal heart rate decelerations
23. Presence of delivery within 1 hour of procedure
24. VAS pain score immediately prior to ECV (-3 minutes)
25. VAS pain score immediately after insertion of Fetal Pillow (+ 2 minutes)
26. VAS pain score after inflation/sham inflation (+ 1 minute)
27. VAS pain score immediately after each ECV procedure attempt, maximum of 4 attempts (+ 2 minutes)
28. Total number of attempts
29. Procedure successful Y N (Primary Outcome) *confirmed by ultrasound
30. Fetal head position post ECV *confirmed by ultrasound
31. Number of forward rolls
32. Number of reverse rolls
33. Note which procedure was successful

34. Did patient request to have spinal or epidural anesthesia after initiation of ECV procedure (off of study protocol): Y N
35. Presence of regional anesthesia prior to ECV procedure (Excluded from study)
36. Length of time from start of procedure to hospital discharge
37. Cost of hospital stay for ECV procedure

Study Design

Research Design

This is a prospective, randomized double-blind clinical trial evaluating the effect of a balloon device to elevate the fetal buttocks during external cephalic version procedures. Eligible study population: pregnant women between 37-40 weeks estimated gestational age with a breech presenting baby and no contraindications to ECV.

Study Agent, Device, and/or Intervention Description:

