Regardless of randomization, at this point the ECV procedure proceeds using normal routine. Once completed, all patients will mark a line on a 100mm VAS to assess post-ECV pain. The ECV will be attempted up to four times and VAS will be assessed after each attempt.

The research physician will then remove the Fetal Pillow and perform a post procedural ultrasound to verify fetal position. Regardless of randomization, the procedure is completed per the usual routine of fetal monitoring, assessing for labor or bleeding, discussing post-procedure care, then discharge home (or, less likely, admitting for either observation or delivery).

The researcher will fill out the ECV portion of the data collection form.

Visit 2 (Labor and Delivery): There are no study interventions during this visit. The file linking the subject's FIN and study numbers will be sent to the honest broker who will then extract the data for delivery outcomes for the mother and neonate along with the final cost calculations. This data will be entered into a spreadsheet by the honest broker and then sent back to the research team. The research team will send the file linking the subject's FIN and study numbers at the intervals outlined in the safety monitoring plan (first 10 randomized subjects and every 20 subjects thereafter). The investigators are unblinded to patient randomization after the ECV procedure has been completed and during data collection for delivery and neonatal outcomes.

Data collection for patients delivering outside of AdventHealth facility. Patients will sign a release of records; study coordinator will request records from delivering facility and delivery outcomes data will be imported into spreadsheet linked to FIN.

Study Duration:

Estimated date of study completion: March 31, 2023

- Projected start date: November 1, 2020.
- Projected completion of enrollment of all study subjects: November 1, 2022.
- Projected final data collection date: March 1, 2023.

Materials of Human Origin: N/A

Study Outcome Measures (Endpoints)

Primary Outcome:

Proportion of patients undergoing ECV who have a successful outcome with and without an inflated Fetal Pillow.

Secondary Outcomes:

As noted, many of these data points are normally recorded in the medical record during an ECV procedure and subsequent delivery, regardless of study participation.

Subject Information (maternal):

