Demographic information of the patient will be collected in the electronic medical record (EMR) by noting ethnicity, number and type of prior deliveries, and measuring height and weight.

Subject Information (neonatal):

Neonatal gestational age at delivery, weight, 1 and 5 minute Apgar scores will be recorded from the medical record..

Pain perception:

Patients will complete a VAS pain scale prior to and after the ECV procedure as well as after the insertion of the fetal pillow and after the inflation/sham inflation of the pillow.

Impact of maternal parameters on successful ECV:

Researchers will measure the distance from the inferior aspect of the ribs to the pubic symphysis using a tape measure, location of placenta by performing an obstetric sonogram, and cervical dilation by performing a digital cervical examination.

Impact of fetal parameters on successful ECV:

A digital vaginal examination will determine the location of the fetal buttocks in the pelvis. The fetal head will be assessed to determine if it can be palpated on abdominal exam. The physician will perform an obstetric ultrasound and measure estimated fetal weight, amniotic fluid index, and position of the fetal neck.

Outcome of ECV procedure: Researchers will document the fetal heart rate pattern, and whether bleeding, contractions, labor, or rupture of membranes occur. If rupture of membranes is suspected, it will be confirmed by sterile speculum examination and testing of the amniotic fluid for ferning or nitrazine. The number and type of ECV maneuvers will be recorded. Bleeding, development of a vaginal hematoma, and delivery within an hour of performing the ECV procedure will be recorded.

Delivery Outcome (maternal):

Researchers will record the fetal presentation at labor admission, type of delivery, whether there was a shoulder dystocia, and the blood loss as measured by weighing any saturated sponges from the medical record.

Delivery Outcome (neonatal):

Researchers will measure the neonatal weight, 1- and 5-minute Apgar scores, whether the baby was stillborn, had a bone fracture, or was intubated and/or admitted to the neonatal intensive care unit from the medical record.

Length of Stay:

Researchers will record the length of stay for mothers for the ECV procedure, and length of stay for both mothers and neonates for the admission for delivery, all measured in hours.

Cost of Stay:

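### The post-inflation pain score is marked while the unblinded inflator is still in the room, so this secondary score is open to cues of unknown size

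*Combined protocol and SAP*

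**What the plan says.** The sequence is set out under Study Visits, Visit 1 (ECV Procedure).

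- Allocation: "The midwife/physician performing the device inflation or sham inflation will open the randomization envelope". The Randomization section also describes the person who fetches the envelope as unblinded.
- The study physician inserts the device in every patient, and she marks a post-insertion score. To keep the operator blinded, "the physician will leave the room during the time of the inflation/sham inflation".
- The assistant inflates the device with 180 mL of saline or performs a sham. On the patient's side, "This will occur under a sheet so that the patient is blinded to the randomization scheme".
- The next step is the score: "All patients will mark a line on a 100mm VAS to assess post-inflation/sham inflation pain".
- The step after that is the change of staff: "The assisting midwife/physician then leaves the room, and the study physician reenters the room and proceeds with the ECV procedure".

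Procedural Outcomes, item 26, gives the timing: "VAS pain score after inflation/sham inflation (+ 1 minute". Under Study Outcome Measures (Endpoints), pain perception is one of the secondary outcomes. On recording, Visit 1 says only, after the procedure is over: "The researcher will fill out the ECV portion of the data collection form". No section names who hands over, explains or collects any of the pain scores.

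**The concern.** The Research Design section describes the trial as double-blind, and Visit 1 protects this with a sham, a sheet and the operator's absence from the room. The post-inflation score falls outside that protection. When the patient marks it, the blinded physician is outside and the one clinician whom the text places with her knows the arm.

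Pain on a 100 mm line is subjective. Tone, reassurance or a leading question could move it. An inflator who expects discomfort might prompt a higher mark in the inflated arm, while one who reassures might hide a real difference. A cue could also tell the patient her arm before she gives the later scores. At stake is the comparison that isolates the pain of inflation from the pain of the version.

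**Working it through.** The claim concerns the order of steps, so the main check is to set the pain scores side by side.

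| Score (Procedural Outcomes) | Arms already diverged? | Version pain included? | Inflator's presence, from Visit 1 |
|---|---|---|---|
| Item 24, before the procedure | No | No | Not stated |
| Item 25, after insertion | No (device inserted in all) | No | Not stated; the assistant's help is obtained after this score |
| Item 26, after real or sham inflation | Yes | No | Present; leaves only after the mark |
| Item 27, after each attempt (up to four) | Yes | Yes | Has left |

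Three things follow.

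1. Item 26 is the only score for which the arms differ and no version has yet been attempted.
2. It is also the only post-divergence score that the text places before the inflator's exit. The word for the order of events in the exit sentence puts that exit after the mark, and a target of one minute after inflation fits this reading.
3. Nothing elsewhere closes the gap. Visit 1 says that inflators have been trained but does not say that training covers neutral conduct while the score is marked. The data form is mentioned only at the end of the procedure.

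The plan has no figure of its own to reproduce here. A conditional calculation shows what a cue would do if it existed. Inputs: n = 69 per arm and two-sided 5% (Sample Size Determination). The standard deviation, SD, and the systematic between-arm cue effect, b, are assumptions with no source in the documents. The true difference is taken as zero.

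- SE = SD × √(2/69), which is 3.4 mm for SD 20 and 4.3 mm for SD 25.
- False-positive rate = Φ(−1.96 + b/SE) + Φ(−1.96 − b/SE).

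| Assumed SD | b = 3 mm | b = 5 mm |
|---|---|---|
| 20 mm | 14.3% | 31.2% |
| 25 mm | 10.9% | 21.7% |
| 30 mm | 9.0% | 16.5% |

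With b = 1 mm the rate is 5.4% to 6.0% across SD 20 to 30 mm. The answer therefore runs from negligible to large, depending wholly on the assumed inputs.

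**The case against.** The strongest reply is that nobody unblinded rates anything. The patient marks the line herself, behind a sheet intended to keep her blinded, and the inflators are trained. The text documents the inflator's presence but not any prompting, and it does not say who else is in the room. Pain is a secondary outcome, and item 26 is one entry among 26 + 11 + 37 = 74 listed items. All of this stands, and it limits the weight of the point. It does not close the gap, because a self-marked score can still be influenced and no rule covers the inflator's conduct.

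A second reply concerns the remedy. It would be natural simply to bring the blinded physician back before the mark. That would let the operator watch the patient's reaction, and perhaps see her score, just before the version whose success is the primary outcome. The present order gives the operator some protection, and a remedy should not spend it. This objection stands in full.

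Third, the inflator has to be with the patient during inflation whatever the order of steps, and 180 mL may be felt whoever is present. Changing the moment of marking cannot remove either channel. This also stands, and it is why a script matters more than the order alone.

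A reader might also take item 26 to be the measure of the pain risk named under Potential Risks. That section speaks of greater pain while the procedure is under way. Item 27 captures this too, after the inflator has gone. Item 26 isolates the narrower question of inflation pain.

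**Conclusion.** The point holds as a modest gap in blinding. As Visit 1 is written, the first pain score after the arms diverge, and the only one free of version pain, is marked in the presence of someone who knows the arm, with no script and no blinded person assigned to the score. Bias is possible in either direction.

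Its size cannot be given. A reader might infer from the conditional figures that the test on item 26 has a false-positive rate of 11% to 31% (SD 20 to 25 mm, cue 3 to 5 mm). The documents do not support that. Those rates restate an assumed SD and an assumed cue that works the same way across inflators, and they suppose that 180 mL causes no pain difference at all. Nor do they describe the opposite error, in which reassurance masks real pain.

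A reader might also infer that the trial's main result is compromised. It is not by this route: success of the version is confirmed by ultrasound. The conclusion rests on reading the Visit 1 steps as sequential, and on the absence of any separate instruction on who administers the score.

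**What to change.** Amend Study Visits, Visit 1 (ECV Procedure), in two respects.

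1. Require one fixed, neutral script, identical in both arms, for everything the inflator says to the patient during and after the real or sham inflation.
2. Have the patient mark the post-inflation score privately once the inflator has stepped away, and cover or seal the form before the study physician re-enters. The blinded operator then sees neither the act of rating nor the mark.

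The cost is a few sentences of protocol text and a short script, with no added staff. The mark may come some seconds later, so the one-minute window of item 26 may need slight widening. The change reduces cueing by the inflator. It does not prevent a patient from recognising her arm by the sensation of inflation, and the report of the pain results should say so.
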